### 8.3.2. Maternal secretory immunity

Summaries and analysis of immunogenicity data will be presented by treatment group for maternal secretory immunity at time of delivery, at 6 weeks after delivery, at 10 weeks (in half of women) or 18 weeks (in half of women) after delivery, and 6 months after delivery. Immune responses to breast milk IgG and IgA antibodies to Tdap vaccine antigens (PT, FHA, PRN, tetanus, and diphtheria) as measured by ELISA will be summarized. Analysis will include GMCs along with corresponding 95% confidence intervals. The GMC between treatment groups will be compared using a t-test on log-transformed ELISA titers ([Table 29](#), [Table 30](#), [Table 31](#), and [Table 32](#)).

RCD curves for maternal subjects will be presented for Breast Milk IgG and IgA antibody concentrations to PT, FHA, PRN, tetanus, and diphtheria. Plots will be generated with five panels (At Delivery, 6 Weeks After Delivery, 10 Weeks After Delivery, 18 Weeks After Delivery, and 6 Months After Delivery), and separate

curves within each panel for each treatment group, as shown in [Figure 37](#), [Figure 38](#), [Figure 39](#), [Figure 40](#), [Figure 41](#), [Figure 42](#), [Figure 43](#), [Figure 44](#), [Figure 45](#), [Figure 46](#), [Figure 47](#), [Figure 48](#), [Figure 49](#), [Figure 50](#), [Figure 51](#), [Figure 52](#), [Figure 53](#), [Figure 54](#), [Figure 55](#), and [Figure 56](#).

Log-transformed Breast Milk IgG and IgA concentrations to PT, FHA, PRN, tetanus and diphtheria for maternal subjects will be plotted over time by treatment group along with the geometric mean at each time point ([Figure 91](#), [Figure 92](#), [Figure 93](#), [Figure 94](#), [Figure 95](#), [Figure 96](#), [Figure 97](#), [Figure 98](#), [Figure 99](#), [Figure 100](#), [Figure 101](#), [Figure 102](#), [Figure 103](#), [Figure 104](#), [Figure 105](#), [Figure 106](#), [Figure 107](#), [Figure 108](#), [Figure 109](#), and [Figure 110](#).) The GMCs and 95% confidence intervals of log-transformed serum IgG and IgA antibodies to each antigen will be plotted over time by treatment group in [Figure 145](#), [Figure 146](#), [Figure 147](#), [Figure 148](#), [Figure 149](#), [Figure 150](#), [Figure 151](#), [Figure 152](#), [Figure 153](#), [Figure 154](#), [Figure 155](#), [Figure 156](#), [Figure 157](#), [Figure 158](#), [Figure 159](#), [Figure 160](#), [Figure 161](#), [Figure 162](#), [Figure 163](#), and [Figure 164](#).

### 8.3.3. Maternal cytokine responses

Summaries and analysis of immunogenicity data will be presented by treatment group for maternal cytokine responses at one month before and after receiving Tdap or Td. Cytokines produced by peripheral blood stimulated with DTwP vaccine antigens will be measured by multiplex assays. Cytokines measured will include Interferon (IFN)- $\gamma$ , Interleukin (IL)-10, IL-12p70, IL-12/IL-23p40, IL-13, IL-15, IL-16, IL-17A, IL-1 $\alpha$ , IL-1 $\beta$ , IL-2, IL-4, IL-5, IL-6, IL-7, IL-8, Tumor Necrosis Factor (TNF)- $\alpha$ , and TNF- $\beta$ . Analysis will include GMCs and corresponding 95% confidence intervals, median, first quartile (Q1), third quartile (Q3), minimum, and maximum for each cytokine at each time point as well as for the change in cytokine concentration between the time points ([Table 33](#) and [Table 34](#)).

Concentrations of each cytokine will be plotted over time by treatment group in [Figure 175](#), [Figure 176](#), [Figure 177](#), [Figure 178](#), [Figure 179](#), [Figure 180](#), [Figure 181](#), [Figure 182](#), [Figure 183](#), and [Figure 184](#). The GMCs and 95% confidence intervals of the concentrations of each cytokine will be presented over time by treatment group in [Figure 195](#), [Figure 196](#), [Figure 197](#), [Figure 198](#), [Figure 199](#), [Figure 200](#), [Figure 201](#), [Figure 202](#), [Figure 203](#), and [Figure 204](#). The change in cytokine concentration will be plotted for the post-baseline time point by treatment group in [Figure 215](#), [Figure 216](#), [Figure 217](#), [Figure 218](#), [Figure 219](#), [Figure 220](#), [Figure 221](#), [Figure 222](#), [Figure 223](#), and [Figure 224](#).

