11.4.3. Immunogenicity Data (ELISA)

Immunogenicity data summaries and analysis for pregnant women will be presented for the ITT and the PP populations. Immunogenicity data summaries and analysis for infants will be presented for the infant ITT and infant PP populations.

Immune responses will be reported for antibodies against each of the antigens in the vaccine and at each time point for each subject group- pregnant women receiving BOOSTRIX, pregnant women receiving Td, and the infants of women who received BOOSTRIX or Td while pregnant. GMC and corresponding 95% confidence intervals will be reported.

For each antigen, GMC will be compared between treatment arms using a t-test on log-transformed ELISA titers.

The level of antibody transplacentally transferred will be summarized as the Geometric Mean Ratio (GMR), with corresponding 95% confidence interval, of mother's concentration to infant's concentration for all mother-infant pairs for which both the mother and infant have data at the applicable time point (delivery/birth).

Graphical presentations of immune response may include reverse cumulative distribution (RCD) curves, and longitudinal presentations of GMTs.

To evaluate the association with of maternal immunogenicity cofactors, Maternal and Infant anti-PT ELISA response will be summarized stratified by maternal age (18-29, 30-39 years old), parity (primiparous vs. multiparous), GA at time of vaccination (14-17, 18-21, 22-26 weeks), GA at time of delivery (28-32, 33-36, 37 or more weeks), and infant birthweight, and these cofactors will be evaluated in regression modeling.

Antibody responses in breast milk/colostrum will be evaluated in a similar way to above.

Additional exploratory analyses, including analysis of cytokine response will be described in the statistical analysis plan.

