##### **3.1.3. Exploratory**

###### **Immunogenicity:**

- To assess the effects of maternal age, parity, gestational age (GA) at which the vaccine is given, GA at delivery, and infant birthweight on antibody responses to BOOSTRIX in pregnant women at time of delivery, and in their newborn infants at birth.
- To assess maternal secretory immunity through measurement of breast milk antibodies to Tdap vaccine antigens in women at the time of delivery, at 6 weeks postpartum, at 10 weeks (in ½ of women) or 18 weeks (in ½ of women) postpartum, and at 6 months after delivery.
- To assess the cytokine profile after stimulation in vitro with diphtheria, tetanus and pertussis antigens of peripheral blood mononuclear cells (PBMC) obtained from women before and one month after receiving Tdap or Td.

- To assess the cytokine profile after stimulation in vitro with diphtheria, tetanus, and pertussis antigens of PBMC obtained from infants before the first dose of DTwP (approximately 6 weeks of age) in all subjects, one month after the first dose of DTwP (approximately 10 weeks of age) in ½ of infants, one month after the last dose of DTwP (approximately 18 weeks of age) in ½ of infants, and at 6 months of age in all infants.

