### 8.3.4. Infant cytokine responses

Summaries and analysis of immunogenicity data will be presented by treatment group for infant cytokine responses prior to first dose of DTwP (or umbilical cord blood), one month after the first dose of DTwP (half of subjects), one month after last dose of study vaccine (half of subjects), and at 6 months of age. Cytokines produced by peripheral blood stimulated with DTwP vaccine antigens will be measured by multiplex assays. Cytokines measured will include IFN- $\gamma$ , IL-10, IL-12p70, IL-12/IL-23p40, IL-13, IL-15, IL-16, IL-17A, IL-1 $\alpha$ , IL-1 $\beta$ , IL-2, IL-4, IL-5, IL-6, IL-7, IL-8, TNF- $\alpha$ , and TNF- $\beta$ . Analysis will include GMCs and corresponding 95% confidence intervals, median, Q1, Q3, minimum, and maximum for each cytokine at each time point as well as the change in cytokine concentration from baseline to each time point ([Table 35](#) and [Table 36](#)).

Concentrations of each cytokine will be plotted over time by treatment group in [Figure 165](#), [Figure 166](#), [Figure 167](#), [Figure 168](#), [Figure 169](#), [Figure 170](#), [Figure 171](#), [Figure 172](#), [Figure 173](#), and [Figure 174](#). The GMCs and 95% confidence intervals of the concentrations of each cytokine will be presented over time by treatment group in [Figure 185](#), [Figure 186](#), [Figure 187](#), [Figure 188](#), [Figure 189](#), [Figure 190](#), [Figure 191](#), [Figure 192](#), [Figure 193](#), and [Figure 194](#). The change in cytokine concentration will be plotted for each post-

---

baseline time point by treatment group in [Figure 205](#), [Figure 206](#), [Figure 207](#), [Figure 208](#), [Figure 209](#), [Figure 210](#), [Figure 211](#), [Figure 212](#), [Figure 213](#), and [Figure 214](#).

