**Table 33: Multiplex Assays Stimulated Peripheral Blood Cells Results with 95% Confidence Intervals by Cytokine, Time Point, and Treatment Group -- Maternal Intent-to-Treat Population**

Cytokine	Time Point	Statistic	BOOSTRIX (N=X)	Td (N=X)	Difference
IFN-<math>\gamma</math>					
	Prior to vaccination	n	x	x	--
		GMC (95% CI)	x.x (x.x, x.x)	x.x (x.x, x.x)	x.x, (x.x, x.x)
		Median (Q1, Q3)	x.x (x.x, x.x)	x.x (x.x, x.x)	x.x (x.x, x.x)
		Min, Max	x, x	x, x	x, x
	One month after vaccination	n			
		GMC (95% CI)			
		Median (Q1, Q3)			
		Min, Max			
	Change from prior to vaccination	n			
		Median (Q1, Q3)			
		Min, Max			
IL-10					
	Prior to vaccination	n			
		GMC (95% CI)			
		Median (Q1, Q3)			
		Min, Max			
	One month after vaccination	n			
		GMC (95% CI)			
		Median (Q1, Q3)			
		Min, Max			
	Change from prior to vaccination	n			
		Median (Q1, Q3)			
		Min, Max			
IL-12p70					
	Prior to vaccination	n			
		GMC (95% CI)			
		Median (Q1, Q3)			
		Min, Max			
	One month after vaccination	n			
		GMC (95% CI)			
		Median (Q1, Q3)			

Table 33: Multiplex Assays Stimulated Peripheral Blood Cells Results with 95% Confidence Intervals by Cytokine, Time Point, and Treatment Group -- Maternal Intent-to-Treat Population (continued)

Cytokine	Time Point	Statistic	BOOSTRIX (N=X)	Td (N=X)	Difference
		Min, Max			
	Change from prior to vaccination	n			
		Median (Q1, Q3)			
		Min, Max			
IL-12/IL-23p40					
	Prior to vaccination	n			
		GMC (95% CI)			
		Median (Q1, Q3)			
		Min, Max			
	One month after vaccination	n			
		GMC (95% CI)			
		Median (Q1, Q3)			
		Min, Max			
	Change from prior to vaccination	n			
		Median (Q1, Q3)			
		Min, Max			
IL-13					
	Prior to vaccination	n			
		GMC (95% CI)			
		Median (Q1, Q3)			
		Min, Max			
	One month after vaccination	n			
		GMC (95% CI)			
		Median (Q1, Q3)			
		Min, Max			
	Change from prior to vaccination	n			
		Median (Q1, Q3)			
		Min, Max			
IL-15					
	Prior to vaccination	n			
		GMC (95% CI)			
		Median (Q1, Q3)			
		Min, Max			
	One month after vaccination	n			

Table 33: Multiplex Assays Stimulated Peripheral Blood Cells Results with 95% Confidence Intervals by Cytokine, Time Point, and Treatment Group -- Maternal Intent-to-Treat Population (continued)

Cytokine	Time Point	Statistic	BOOSTRIX (N=X)	Td (N=X)	Difference
		GMC (95% CI)			
		Median (Q1, Q3)			

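### SAP 8.3.3 and its table shell disagree on how to summarise maternal cytokine change, whose scale is undefined, and the one-month arm contrast is not adjusted for the Day 1 value

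*SAP*

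**What the plan says.** The exploratory maternal cytokine objective in SAP 3.1.3 concerns cells from "women before and one month after receiving Tdap or Td". Protocol 11.4.3 leaves the method to the SAP: "Additional exploratory analyses, including analysis of cytokine response will be described in the statistical analysis plan". The SAP is therefore the only place where the analysis is defined.

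SAP 8.3.3 lists the statistics: "Analysis will include GMCs and corresponding 95% confidence intervals, median, first quartile (Q1), third quartile (Q3), minimum, and maximum for each cytokine". The sentence then applies them "for each cytokine at each time point as well as for the change in cytokine concentration between the time points" and cites Tables 33 and 34. The infant text in 8.3.4 is similar but looser: "as well as the change in cytokine concentration from baseline to each time point".

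In the Table 33 shell, the block "Prior to vaccination" and the one-month block each have rows for n, GMC with 95% CI, median with quartiles, and range, by arm and with a Difference column. The block "Change from prior to vaccination" has only n, median with quartiles, and range. This holds for all 18 cytokines. The Table 35 change rows for infants are built the same way.

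No model is given for cytokines. The only covariates named in SAP 6.4 are cofactors of the anti-PT response.

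**The concern.** The question is how each woman's cytokine output moves after vaccination, and whether it moves more with BOOSTRIX than with Td. Change is the only planned quantity that combines a woman's Day 1 value with her later value. Its scale is not defined, the text asks for a statistic that may not exist, and the shell leaves out both that statistic and any interval. Two programmers could build different tables from this SAP, and the choice between them could be made after the data are seen.

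The arm contrast at one month has an interval but does not use the Day 1 measurement of the same cytokine as a covariate. That measurement is already collected. What is lost is precision, and the loss grows with the correlation between the two measurements.

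**Working it through.** The plan gives no sample size, precision or power for cytokines, so there is no stated figure to reproduce.

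**1. Text against shell**

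| Quantity | SAP 8.3.3 text | Table 33 shell |
|---|---|---|
| Day 1 value | GMC with CI, median, quartiles, range | same |
| One-month value | same | same |
| Change | same list, as the sentence is built | n, median with quartiles, range only |

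Elsewhere the SAP names a ratio when it means one (the GMR in 8.2.3) and names log transformation when it means that (8.1, 8.2). For cytokine change it names neither. A difference is the natural reading, but that is an inference.

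**2. Is the geometric mean of a difference computable?**

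Assume lognormal values with log SD σ, correlation ρ between Day 1 and one month, and a true fold rise f. Neither σ nor ρ is in the documents. Then

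P(change ≤ 0) = Φ(−ln f / (σ√(2(1−ρ)))).

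With σ = 1.0 and ρ = 0.5 the denominator is 1.0:

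- f = 1: Φ(0) = 50%
- f = 1.5: Φ(−0.405) = 34%
- f = 2: Φ(−0.693) = 24%
- f = 3: Φ(−1.099) = 14%

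As ρ goes from 0.3 to 0.7, the share is 28% to 18.5% at f = 2 and 18% to 8% at f = 3. Even at f = 3 and ρ = 0.7, the chance that all 67 Td changes are positive is (1 − 0.078)^67 ≈ 0.004. At f = 5 and ρ = 0.7 it is 0.28. So a geometric mean over all subjects would exist only by luck, unless responses were large. If change is a ratio, the geometric mean exists whenever both values are positive.

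**3. What does adjustment gain in mothers?**

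On the log scale, the variance factor of the arm contrast is 1 for the one-month value alone, 2(1−ρ) for log change, and 1−ρ² with the log Day 1 value as covariate. The standard error is σ√(factor × (1/133 + 1/67)). With the planned 133 and 67 women and σ = 1.0, √(0.00752 + 0.01493) = 0.150, and the unadjusted 95% half-width is 0.294.

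| ρ (assumed) | One-month only | Log change | Adjusted | Variance cut | CI narrower by |
|---|---|---|---|---|---|
| 0.3 | 0.294 | 0.347 | 0.280 | 9% | 5% |
| 0.5 | 0.294 | 0.294 | 0.254 | 25% | 13% |
| 0.7 | 0.294 | 0.227 | 0.210 | 49% | 29% |

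The last two columns do not depend on σ. With 15% loss (113 and 57; the SAP gives that rate for the primary outcome, not for cytokines), the half-widths at ρ = 0.5 are 0.318 unadjusted and 0.276 adjusted. Comparing log change between arms is not a substitute: at ρ = 0.3 it is less precise than ignoring baseline.

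**4. Does the same adjustment suit infants?**

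The infant starting value is the pre-DTwP sample at about 6 weeks, or cord blood. Both follow the mother's randomisation and vaccination. Suppose the arm shifts that log value by 0.3 and acts on the later value only through it, with coefficient 0.5 (both assumed). The unadjusted arm effect is 0.3 × 0.5 = 0.15. The adjusted effect is 0. Adjustment would remove the effect being studied.

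**The case against.** The strongest reply is that the shell is the output specification, and it leaves out the GMC exactly where it could be undefined. On that view only loose wording in 8.3.3 is at fault, and the infant sentence in 8.3.4 can be read as simply adding change to the list. This has force. It turns the point into a conflict between text and shell, not a settled plan to compute an impossible statistic. It does not remove the conflict, and following the shell leaves change with no interval estimate.

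Four stronger readings are tempting, and the documents do not support them.

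- A reader might infer that the baseline value is used only through change. It is not: Table 33 summarises it by arm with a Difference column, and 8.3.3 adds plots: "The GMCs and 95% confidence intervals of the concentrations of each cytokine will be presented over time by treatment group".
- A reader might infer that women with non-positive changes will be dropped, so that both arms appear to respond. No section says so.
- A reader might infer a loss of power. SAP 6.8 says that no specific null hypothesis is tested, and no cytokine p-value or power is planned, so only precision can be discussed.
- A reader might extend the baseline-adjusted model to infants. Their baseline follows the mother's vaccination, and Protocol 2.1.5 gives the possible effect of maternal immunisation on infant T-cell responses as the reason for measuring them.

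**Conclusion.** The point holds as a minor one. Read literally, SAP 8.3.3 asks for a GMC with CI of a change whose scale it does not define, and the Table 33 and 34 change rows provide neither. If change is a difference, that GMC is in practice not computable for modest responses. Separately, the one-month maternal contrast forgoes a variance reduction of 1−(1−ρ²) = ρ², that is 9%, 25% or 49% at correlations of 0.3, 0.5 or 0.7. Those correlations and the log SD of 1.0 are assumptions.

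Because the arms are randomised, the unadjusted contrast is unbiased, and the endpoint is exploratory and descriptive. No primary or secondary conclusion is affected.

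**What to change.** **Mothers (SAP 8.3.3, Tables 33 and 34).** Define change as log(post/pre). Report the geometric mean fold change with 95% CI by arm. Add the BOOSTRIX/Td ratio with 95% CI from a linear model of the log one-month value on arm and log Day 1 value. State in advance how zero or below-detection values are handled, since a log ratio also fails when either value is zero. Keep the median and range rows as description.

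**Infants (SAP 8.3.4, Tables 35 and 36).** Adopt only the fold-change definition, with its 95% CI and the same rule for zero or below-detection values. Leave the arm contrasts unadjusted.

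**Cost.** The changes are to wording and shells. No new data are needed, and SAP 8.3.1 already fits models to log titres and exponentiates them to ratios with CIs. The downside is that women without a Day 1 value drop out of the adjusted contrast, as they already do from any change summary. The unadjusted one-month rows remain in the table for them.

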### 8.3.4. Infant cytokine responses

Summaries and analysis of immunogenicity data will be presented by treatment group for infant cytokine responses prior to first dose of DTwP (or umbilical cord blood), one month after the first dose of DTwP (half of subjects), one month after last dose of study vaccine (half of subjects), and at 6 months of age. Cytokines produced by peripheral blood stimulated with DTwP vaccine antigens will be measured by multiplex assays. Cytokines measured will include IFN- $\gamma$ , IL-10, IL-12p70, IL-12/IL-23p40, IL-13, IL-15, IL-16, IL-17A, IL-1 $\alpha$ , IL-1 $\beta$ , IL-2, IL-4, IL-5, IL-6, IL-7, IL-8, TNF- $\alpha$ , and TNF- $\beta$ . Analysis will include GMCs and corresponding 95% confidence intervals, median, Q1, Q3, minimum, and maximum for each cytokine at each time point as well as the change in cytokine concentration from baseline to each time point ([Table 35](#) and [Table 36](#)).

Concentrations of each cytokine will be plotted over time by treatment group in [Figure 165](#), [Figure 166](#), [Figure 167](#), [Figure 168](#), [Figure 169](#), [Figure 170](#), [Figure 171](#), [Figure 172](#), [Figure 173](#), and [Figure 174](#). The GMCs and 95% confidence intervals of the concentrations of each cytokine will be presented over time by treatment group in [Figure 185](#), [Figure 186](#), [Figure 187](#), [Figure 188](#), [Figure 189](#), [Figure 190](#), [Figure 191](#), [Figure 192](#), [Figure 193](#), and [Figure 194](#). The change in cytokine concentration will be plotted for each post-

---

baseline time point by treatment group in [Figure 205](#), [Figure 206](#), [Figure 207](#), [Figure 208](#), [Figure 209](#), [Figure 210](#), [Figure 211](#), [Figure 212](#), [Figure 213](#), and [Figure 214](#).

## 9. SAFETY EVALUATION

All summaries and analysis of safety data will be presented for the Safety Analysis Population. Safety summaries will be presented overall and by treatment group.

Listings will be sorted by maternal or infant, treatment group, subject ID, parameter (if applicable), and visit.

Continuous variables will be summarized using the following descriptive statistics: n (non-missing sample size), mean, standard deviation, median, maximum and minimum. All categorical measures will be summarized by the frequency and percentages (based on the non-missing sample size) of observed levels. The denominator for the percentages may be based on the number of non-missing observations for an assessment or based on the number of subjects in a population. This will be described for each table.

### 9.1. Demographic and Other Baseline Characteristics

Summaries of maternal age, ethnicity, other ethnic group, race, maternal age, and GA at vaccination will be presented by treatment group and overall in [Table 15](#) (categorical characteristics) and [Table 16](#) (continuous characteristics). Summaries of infant, sex, ethnicity, other ethnic group, race, GA at birth, delivery, Apgar score (1, 5 and 10 minutes), birth weight, length at birth, and head circumference at birth, will be presented by treatment group and overall in [Table 17](#) (categorical characteristics) and [Table 18](#) (continuous characteristics). Ethnicity is categorized as Hispanic or Latino, or not Hispanic and not Latino. In accordance with NIH reporting policy, subjects may self-designate as belonging to more than one race or may refuse to identify a race, the latter reflected in the case report form (CRF) as “No” to each racial option.

Individual subject listings ([Appendix 3](#)) will be presented for all demographics ([Listing 5](#) and [Listing 6](#)).

#### 9.1.1. Prior and Concurrent Medical Conditions

Complete medical history will be obtained by interview of subjects at the screening visit and will be reviewed and/or updated on Day 1 prior to study vaccination. Subjects will be queried regarding a history of significant medical disorders of the head, eyes, ears, nose, throat, mouth, cardiovascular system, lungs, gastrointestinal tract, liver, pancreas, kidney, urologic system, nervous system, blood, lymph nodes, endocrine system, musculoskeletal system, skin, and genital/reproductive tract. A history of any allergies, cancer, immunodeficiency, psychiatric illness, substance abuse, and autoimmune disease will be solicited.

All current illnesses and pre-existing medical conditions will be MedDRA® coded using MedDRA dictionary version 21.0 or higher. Summaries of subjects' pre-existing medical conditions will be presented by treatment group ([Table 19](#) and [Table 20](#)).

Individual subject listings will be presented for all medical conditions ([Listing 7](#)).

